4.2 Secondary Outcomes

Secondary outcome analysis will include systolic and diastolic blood pressure parameters to assess cardiovascular responses to the interventions. Descriptive statistics (mean \pm standard deviation) will be computed for each time point within and between groups.

A repeated measures ANOVA will be performed to examine within-group changes across time and between-group differences in blood pressure values. Where significant effects are identified, post-hoc analysis with Bonferroni adjustment will be carried out to explore pairwise differences between baseline, 2nd week, and 4th week measurements. In cases of sphericity violation, the Greenhouse-Geisser correction will be applied. Statistical significance will be set at $p < 0.05$.

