3.1 Research Design Outline

The study aims to perform a Comparative study on older people who have been immobilized due to femur neck fractures.in Saveetha Medical College and Hospital.

Formerly titled “Effectiveness of Liuzijue and Box Breathing Techniques on Inspiratory Capacity and Blood Pressure Following Femoral Neck Fracture Immobilization: A Retrospective Comparative Study” involves elderly with femoral neck fracture immobilization by Inspiratory capacity and blood pressure were assessed using a volumetric incentive spirometer and a digital sphygmomanometer, respectively. Improvement in inspiratory capacity was defined as an increase in measured values, with ranges progressing from approximately 1300 mL to 3000 mL. Improvement in cardiovascular status was considered when blood pressure remained within a stable range, with systolic values between 120-150 mmHg and diastolic values between 70-90 mmHg.

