3.3 Recruitment

For this retrospective analysis, medical and physiotherapy records of patients with femoral neck fracture immobilization treated at the Saveetha Medical College and Hospital were reviewed.

Records of participants who had completed a four-week intervention program and had documented outcome measures were included in the study. No direct recruitment or prospective enrollment was undertaken.

Data related to inspiratory capacity measured using a volumetric spirometer and blood pressure assessed using a digital sphygmomanometer were extracted from patient records. Outcome measures recorded at baseline (pre-intervention), at the second week and at the fourth week were included for analysis. Confidentiality of patient information was maintained and the study procedures were conducted under the approval and supervision of the institutional ethics committee and the principal investigator.

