3.5.2 Secondary outcomes

- Blood Pressure - Digital Blood Pressure Monitor (Digital Sphygmomanometer)
 - To measure systolic and diastolic blood pressure. To evaluate cardiovascular response to breathing interventions. To monitor physiological changes over the intervention period
 - Automated, non-invasive device using Oscillo metric methods.
 - Consists of inflatable cuff and digital display.
 - Blood pressure recorded after adequate rest

4. Statistical Analysis Plan (SAP)

Descriptive and inferential statistics will be used. Normally distributed data will be presented by mean and standard deviation (SD) and non-normally distributed data will be presented by median and interquartile range. Categorical data will be presented using percentages. SPSS (version 27.0) will be used for all statistical analyses.

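### Blood pressure change is read as a response to the breathing techniques, but the plan states no extraction or handling of antihypertensive treatment, which could produce the same change

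*Combined protocol and SAP*

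**What the plan says.** Section 3.5.2 gives one purpose of measuring blood pressure as: "To evaluate cardiovascular response to breathing interventions". Section 4.2 repeats the aim: "Secondary outcome analysis will include systolic and diastolic blood pressure parameters to assess cardiovascular responses to the interventions". The method follows: "A repeated measures ANOVA will be performed to examine within-group changes across time and between-group differences in blood pressure values". No covariate is named. Section 4.1, which sets out the factors for the parallel primary analysis, lists only time and group.

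On data, section 3.3 states: "Data related to inspiratory capacity measured using a volumetric spirometer and blood pressure assessed using a digital sphygmomanometer were extracted from patient records". It takes readings at baseline, week 2 and week 4, and describes the design in these words: "No direct recruitment or prospective enrollment was undertaken". Section 3.2 says that patients were found by reviewing medical and physiotherapy records and had received one technique or the other. It refers to eligibility criteria but does not list them.

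Section 3.1 also gives a reading rule: "Improvement in cardiovascular status was considered when blood pressure remained within a stable range", with systolic limits of 120 to 150 mmHg and diastolic limits of 70 to 90 mmHg. It sets no condition on drug treatment.

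No section mentions antihypertensives, concomitant drugs, covariate adjustment, stratification or a sensitivity analysis.

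**The concern.** Antihypertensive treatment acts directly on this outcome, and the plan's own background makes it plausible here. Section 2.1 says that immobilisation raises the risk of hypertension, and section 2.2 cites frequent cardiovascular comorbidity in patients with this fracture. Over four weeks of routine care, some patients may start, stop or change treatment.

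The design does not separate that from breathing. With no untreated arm, a time effect within a group mixes the technique with everything else that changes over four weeks. With treatment as received, nothing balances drug use or drug changes between the groups. Section 2.1 does call the study randomised, which conflicts with sections 3.1 to 3.3. Even if that label were right, the within-group reading would remain confounded.

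At stake is the blood pressure conclusion. A fall in either group, or a difference between groups, could be reported as a technique effect although the plan had been followed exactly.

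**Working it through.** **No figure to reproduce.** The document gives no sample size, SD, expected effect, drug-change rate or drug effect. Everything below is an illustration of direction and possible size. The significance level of 0.05 is from section 4.2; a two-sided test is assumed because the document does not say. The true technique effect is set to zero.

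**Between groups.** Assumptions: SD of change from baseline to week 4 is 12 mmHg; the shares with a drug change differ by 20 percentage points; a change is worth 10 mmHg; n is 20, 30 or 50 per group.

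- Bias = difference in shares × effect per change = 0.20 × 10 = 2 mmHg.
- Standard error = 12 × √(2/n) = 3.79, 3.10, 2.40 mmHg.
- Non-centrality = 2 / standard error = 0.53, 0.65, 0.83.
- False-positive rate (non-central t, 2n − 2 degrees of freedom) = 8.1%, 9.7%, 13.1%.
- No imbalance: bias = 0 × 10 = 0, and the rate stays at 5%.
- Range, for differences of 10 to 30 points and effects of 5 to 15 mmHg: bias from 0.10 × 5 = 0.5 to 0.30 × 15 = 4.5 mmHg; rate from 5.2% (smallest bias, n = 20) to 46% (largest bias, n = 50).

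**Closer to the planned test.** The figures above are for a two-group test of change, whereas the plan is an ANOVA over three time points. Assume compound symmetry and a linear build-up of the bias (0, 1, 2 mmHg).

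- Residual variance = 144 / 2 = 72.
- Non-centrality of the group-by-time F test = (n/2) × [(−1)² + 0² + 1²] / 72 = n/72 = 0.28, 0.42, 0.69, with 2 and 4(n − 1) degrees of freedom.
- False-positive rate = 7.1%, 8.2%, 10.5%. The 46% extreme becomes about 37%.

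**Within one group.** Assume that 30% have a drug change worth 10 mmHg, with SD 12 mmHg.

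- Mean shift = 0.30 × 10 = 3 mmHg.
- Standard error = 12 / √n = 2.68, 2.19, 1.70 mmHg; non-centrality = 1.12, 1.37, 1.77.
- Rate of a significant within-group change = about 19%, 26%, 41% for n = 20, 30, 50.

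**Second set of assumptions.** Use a normal approximation, a base SD of 10 mmHg, and the extra variance q(1 − q)e² that arises because only a share q of patients shift by e. With 30 per group:

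- 30% changing in a group: the within-group rate is 13% (e = 5 mmHg) or 32% (e = 10 mmHg). The time effect over both groups together is 21% or 56%.
- 30% against 10% changing: the between-group rate is 7% or 11%.
- 30% in both groups: the between-group rate is 5%.

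Both sets point the same way. The within-group reading is the more exposed. The between-group reading is affected only when drug treatment differs by group.

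**The case against.** The strongest reply has four parts.

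- **The plan may collect more than it names.** Section 3.3 does not say that the two outcomes are the only data extracted, section 4 plans percentages for categorical data, and the unlisted eligibility criteria could contain a drug condition. This stands as a limit on wording: a reader might infer that drug data will not be collected, but the document shows only that none is named and no handling is stated.
- **The size is assumed.** This stands. The central case is modest, and the 46% needs a 30-point imbalance, 15 mmHg per change and 50 per group together. A reader might take that as the expected error rate, or conclude that the group comparison is biased in any event. The document supports neither, since it gives no rate of drug change and no sign of imbalance.
- **Drug data would not rescue a within-group claim.** This also stands. Recovery, regression to the mean and other time trends would still confound it without an untreated arm. The remedy must therefore restrict how within-group change is read, not only add covariates.
- **This is one instance of a wider lack of confounder adjustment, on a secondary outcome.** That is fair as to weight. The point still needs its own remedy, because a baseline covariate cannot capture drug changes made after baseline.

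The in-range rule in section 3.1 is weak support for the concern: section 4.2 analyses blood pressure values and does not use it.

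**Conclusion.** The concern holds in limited form. The plan reads blood pressure change as a response to breathing, names no drug data and states no handling of antihypertensive treatment, in a retrospective as-received comparison with no untreated arm. Drug treatment can therefore produce a within-group change, and can produce a between-group difference if use or changes differ by group.

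The possible size is known only by assumption. With 20 to 50 per group, the between-group false-positive rate is about 8% to 13% in the central case (about 7% to 11% for the three-time-point test) and 5% with no imbalance. In the within-group example it is about 19% to 41%.

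A reader might infer that drugs do explain any blood pressure result. The document does not show that; it shows only that the plan could not tell the two explanations apart. The change should be made, but it concerns a secondary outcome and leaves the inspiratory capacity analysis untouched.

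**What to change.** **Section 3.3.** Add to the extraction list antihypertensive use at baseline, and any dated start, stop or change up to the week-4 reading, where the medical records hold it. Report by group how often this information is missing.

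**Section 4.2.**

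- Adjust the between-group blood pressure comparison for baseline antihypertensive use and baseline blood pressure.
- Tabulate drug changes by group.
- Add an analysis limited to readings taken before any drug change, labelled as a supportive sensitivity analysis. It conditions on a post-baseline event that may itself respond to blood pressure, so its agreement with the adjusted analysis should not be made a condition for attributing a difference to technique.
- State that within-group blood pressure change will be reported descriptively and not as an effect of either technique. Align the purpose given in section 3.5.2 with this.

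**Cost.** A few more fields from records already under review, one table, one adjusted model and one sensitivity analysis with fewer readings. Section 4.3 already expects incomplete records, so the drug data may have gaps, and dated changes may not be recoverable for every patient. The blood pressure conclusion will be more cautious.

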4.3 Missing Data

In the event of missing data due to incomplete clinical records, appropriate statistical handling will be undertaken. Where feasible, missing values will be addressed using mean imputation within the respective intervention group, provided the proportion of missing data is minimal and missing at random. Cases with substantial missing data will be excluded from the final analysis.

4.4 Informed Consent Forms (ICF)

Written informed consent had been obtained from participants at the time of clinical treatment as part of routine hospital protocol. For the present analysis, waiver of fresh informed consent will be sought from the Institutional Ethics Committee, as the study involves reviewing existing medical and physiotherapy records without direct participant contact.

4.4.1 Rights and Risks to participants

Rights

Participants' rights to autonomy, dignity and confidentiality will be fully respected. Participation in the retrospective analysis will not affect the standard of care received by the patients. Individuals retain the right to withdraw their clinical data from analysis if required by institutional policy. No remuneration or reimbursement is associated with participation in this study.

Risks

No foreseeable physical, psychological or social risks are anticipated, as the study involves secondary analysis of previously collected clinical data and does not include any additional interventions or assessments.

